2.3 INTERVENTIONS

The patients will be recruited in the Oral Medicine Department, in a 12 months period.

Study design (see flow-chart)

A baseline visit (T_0) will be conducted three months after the end of RT.

The investigational product GUM Hydral and the placebo will be each administered for a 30-days treatment period.

The patients will be divided into two groups: at **day 1 (baseline - T_0)**, group A will receive treatment product, group B will receive a placebo.

At **day 15**, the compliance of the patient and any adverse effect will be evaluated by a phone call.

At **day 30**, the administration of the products will be stopped, and a 30 days washout phase will take part, followed by Phase 2 of the study.

At **day 61**, each group will be treated with the alternative product.

At **day 75**, the compliance of the patient and any adverse effect will be evaluated by a phone call.

At **day 90**, the final questionnaire will be administered, and the investigation of all endpoints will take place.

Each Visit is described in the following flow-chart

Activities/Procedures	Screening Visit (after 3 months from the end of the RT) From Day-3 to Day 0	Baseline Visit Day 1	DAY 15 (± 2 gg)	DAY 30 (± 7 gg)	DAY 31-60 Washout phase	DAY 61	DAY 75	DAY 90 (End of Study Visit) (± 7 gg)
	PHASE A					PHASE B		
Visit	V1	V2	V3	V4	V5 (Note 2)		V6	V7
Informed Consent signature	X							
Inclusion/Exclusion Criteria verification	X							
Randomization		X						
Demography	X							
Medical and surgical history and underlying diseases	X							
Previous and concomitant treatments	X	X		X	X	X		X
Physical examinations	X			X		X		X
Salivary flow measurement	X			X		X		X
Oral swab for mycetes determination	X					X		X
Medical Device administration and accountability (pts compliance to treatment is assessed at each protocol visit) (Note 3)		X (Note 4)	X	X		X (Note 5)	X	X
Diary card dispensing and verification		X	X	X		X	X	X
QoLs administration	X (Note 6)		X	X		X	X	X
AEs monitoring	X	X	X	X	X		X	X

Note1: the screening visit might have a maximum duration of 1 day

Note 2: during the washout period a telephone contact will be conducted, in order to assess the safety profile of the patients, by specifically asking to refer any AE occurred and relevant concomitant medications administered (if applicable)

Note 3: an instruction procedure to standardize the products administration will be finalized. Patients will be asked to rinse with 15 ml of product, three times a day.

Note 4: PHASE A, Group A receives Hydral, Group B receives placebo

Note 5: PHASE B, Group A receives placebo, Group B receives Hydral

Note 6: this QoLS administration must be conducted after the ICF signature and before the first Medical Device administration

2.3.1 STUDY PROCEDURES

VISIT SCHEDULING

- Visit 1: DAY 1
- Visit 2: DAY 15
- Visit 3: DAY 30
- Washout phase: DAY 31-60
- Visit 4: DAY 61
- Visit 5: DAY 75
- Visit 6: DAY 90

DESCRIPTION OF VISITS AND ASSESSMENTS

VISIT 1:

- Informed consent signature
- Inclusion/Exclusion criteria verification
- Medical and surgical history and underlying diseases will be verified
- Previous and concomitant oral treatments will be checked out and proceed regularly, excluding any antitumoral therapy, both radio and chemotherapy
- Physical examination
- Oral swab for mycetes determination will be taken
- Salivary flow, both basal and stimulated, will be measured
- Three questionnaires for the assessment of xerostomia and of the quality of life will be administered:
QLQ30
QLQH&N35
XQ questionnaire. In addition, one question by the Shortened Xerostomia Inventory (SXI-D) scale score will be used
- In addition, xerostomia will be assessed even through a NRS Scale
- Further, the patient's satisfaction in using each product will be evaluated by using a Likert scale
- Drug Administration and accountability: participants will be instructed to rinse with the mouthwash five times per day, especially before going to bed.

VISIT 2:

- Drug Administration and accountability: the compliance of the patient will be evaluated
- AEs monitoring

VISIT 3:

- Previous and concomitant oral treatments will be checked out and proceed regularly
- Physical examination
- Salivary flow measurement (both basal and stimulated)
- Drug Administration and accountability: the compliance of the patient will be evaluated
- Three questionnaires for the assessment of xerostomia and of the quality of life will be administered:
 - QLQ 30
 - QLQ H&N35
 - XQ questionnaire. In addition, one question by the Shortened Xerostomia Inventory (SXI-D) scale score will be used
- In addition, xerostomia will be assessed even through a NRS Scale
- Further, the patient's satisfaction in using each product will be evaluated by using a Likert scale
- AEs monitoring

VISIT 4:

- Previous and concomitant oral treatments will be checked out and proceed regularly
- Physical examination
- Drug Administration and accountability: the compliance of the patient will be evaluated
- Three questionnaires for the assessment of xerostomia and of the quality of life will be administered:
 - QLQ 30
 - QLQ H&N35
 - XQ questionnaire. In addition, one question by the Shortened Xerostomia Inventory (SXI-D) scale score will be used
- In addition, xerostomia will be assessed even through a NRS Scale
- Further, the patient's satisfaction in using each product will be evaluated by using a Likert scale

- Drug Administration and accountability: every patient will receive the product alternative to the one he used during the first phase of the trial
- Oral swab for mycetes determination will be taken
- AEs monitoring

VISIT 5:

- Drug Administration and accountability: the compliance of the patient will be evaluated
- AEs monitoring

VISIT 6:

- Previous and concomitant oral treatments will be checked out and proceed regularly
- Physical examination
- Salivary flow measurement (both basal and stimulated)
- Drug Administration and accountability: the compliance of the patient will be evaluated
- Three questionnaires for the assessment of xerostomia and of the quality of life will be administered:
 - QLQ 30
 - QLQ H&N35
 - XQ questionnaire. In addition, one question by the Shortened Xerostomia Inventory (SXI-D) scale score will be used
- In addition, xerostomia will be assessed even through a NRS Scale
- Further, the patient's satisfaction in using each product will be evaluated by using a Likert scale

2.4 STUDY OBJECTIVES

The measurement of xerostomia is problematic. In contrast to hyposalivation, which can be objectively evaluated by using sialometry, xerostomia is comprised of a set of symptoms, and therefore can be assessed only by directly questioning individuals.

The questionnaire which will be used to this evaluation are Xerostomia Questionnaire (13) (14). To the XQ questionnaire, 1 further question was added from Xerostomia Inventory (XI) scale score (15).

The QLQ-C30 provides 30 questions, globally assessing patients' quality of life. The QLQ-H&N35 includes 35 questions, and addresses symptoms associated with specific tumor location, side effects associated with the oncologic treatment and additional QoL aspects modified by the disease or its treatment. The answers will be converted into a linear scoring scale, with values between 0 and 100, (16) (17) as per advocated by EORTC.

The modified XQ provides a measure of the severity of radiation -induced xerostomia that affects the patients' QoL. This questionnaire consists of 10 questions, associated with patient-reported dryness. Moreover, a general question "how dry is your mouth?" has been added to the questionnaire. The modified XQ is a self-administered tool and patients will be asked to rate each symptom on a 10-point NRS scale of 0-10, with higher scores indicating more severe dryness or discomfort due to dryness. Each item score is added, and the sum is linearly transformed to produce the final summary score ranging from 0 to 100, with higher scores representing higher levels of xerostomia.

Patients' compliance will be evaluated by the use of a diary card, in order to notice the amount of product used.

2.4.1 PRIMARY OBJECTIVE

To describe the results of the five questionnaires (listed below) at all the timepoints:

QLQ 30 (18)

QLQ H&N35 (19)

Xerostomia Inventory (XI) scale score (20) (21)

VAS scale

Xerostomia Questionnaire (22)

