1.3 FEATURES OF THE MEDICAL DEVICE

The device is a high-density liquid and it is used as a mouthwash. In this trial, the aim is to investigate if its efficacy in reducing the xerostomia symptoms is higher than placebo.

The placebo will be made of water with xylitol in addition. Xylitol is a sugar alcohol used as a sugar substitute, which does not increase the risk of tooth decay. In this formulation, its only role is to give a slight sweet flavor to water.

Water added with xylitol, in fact, may reduce, to a certain extent, the xerostomia symptoms, so it may be considered as a suitable comparator.

The device used for the clinical trial will be identified with visible marking stating “Exclusively for clinical investigations SSHNC-1 only”.

Funder will initiate the shipment of the medical device to the site upon the Principal Investigator received the Ethics Committee approval. Prior to any shipment, the site will be informed by the Funder/Sponsor on the upcoming shipment, expected arrival date and content of the shipment. The site should confirm receipt of the shipment.

Funder will also be encharged of the manufacturing and biological stabilization of placebo, whose composition is described above.

The placebo used for the clinical trial will be identified with visible marking stating “Exclusively for clinical investigations SSHNC-1 only”.

Funder will also initiate the shipment of the placebo to the site upon the Principal Investigator received the Ethics Committee approval. Prior to any shipment, the site will be informed by the Funder/Sponsor on the upcoming shipment, expected arrival date and content of the shipment. The site should confirm receipt of the shipment.

For the risk analysis please refer to the IfU (Instruction for Use).

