1.4 PURPOSES AND OBJECTIVES OF THE CLINICAL TRIAL

The aim of this study is to describe the effect of the administration of Hydral on reducing patients' xerostomia symptoms due to radiotherapy. (12)

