2.4.2 SECONDARY OBJECTIVES

- Evaluate Hydral treatment efficacy in reducing xerostomia's symptoms;
- Describe all the adverse events occurred during the study.

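### Section 1.3 asks whether Hydral beats placebo, but the primary objective only describes questionnaire scores; the treatment contrast is implicit and should be stated as primary

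*Combined protocol and SAP*

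**What the plan says.** The document states its aim twice. Section 1.3 is comparative: "the aim is to investigate if its efficacy in reducing the xerostomia symptoms is higher than placebo". Section 1.4, under the heading for purposes and objectives, is not: "The aim of this study is to describe the effect of the administration of Hydral on reducing patients' xerostomia symptoms due to radiotherapy".

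The primary objective (2.4.1) follows the second version: "To describe the results of the five questionnaires (listed below) at all the timepoints". It names no treatment contrast, no single outcome and no hypothesis. Section 2.4.2 has two secondary objectives, "Evaluate Hydral treatment efficacy in reducing xerostomia's symptoms" and "Describe all the adverse events occurred during the study". Neither names the placebo.

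Section 2.8.2 assigns descriptive statistics to the primary objective. In a separate sentence it assigns an ANOVA mixed model to efficacy, without giving the outcome, the timepoint or the contrast.

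Section 1.5 sets up a double-blind randomised crossover in which both groups receive both products. Section 2.8.1 derives N=40 from a 30% difference between treatments in the share of patients who improve, with alpha 0.05 and 80% power. On the comparator, 1.3 says that water with xylitol "may reduce, to a certain extent, the xerostomia symptoms, so it may be considered as a suitable comparator".

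**The concern.** A randomised, blinded crossover exists to estimate one quantity well: the within-patient difference between the two products. Here no listed objective asks for that quantity by name, and the objective ranked first asks only for summaries of five instruments over time. Tables of means at each visit would fulfil it whatever the difference between Hydral and placebo turned out to be.

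The comparator makes this matter more. If the placebo rinse can ease symptoms, a falling score during a Hydral period could come from Hydral's advantage over the rinse, from rinsing as such, or from the passage of time. Only the contrast with placebo separates the first from the others. If that contrast is not the declared primary question, the report has no prespecified main answer to what 1.3 asks. The choice of instrument and timepoint on which to judge superiority is then left until after the data are seen.

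**Working it through.** **1. Which places ask for a comparison?**

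| Section | What it asks for | Placebo contrast |
|---|---|---|
| 1.3 | Efficacy above placebo | Explicit |
| 1.4 | Description of Hydral's effect | Absent |
| 1.5 | Randomised double-blind crossover | Implied by design |
| 2.4.1 (primary) | Description of five questionnaires | Absent |
| 2.4.2 (secondary) | Evaluation of Hydral efficacy | Implied at most |
| 2.8.1 | N for a difference in share improved | Explicit, on an outcome named in no objective |
| 2.8.2, primary | Descriptive statistics | Absent |
| 2.8.2, efficacy | ANOVA mixed model | Implied; not specified |

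The primary objective and its analysis agree with each other and with 1.4. They do not agree with 1.3, 1.5 or 2.8.1.

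**2. Does the primary result depend on the treatment difference?** Suppose Hydral is better than, equal to, or worse than placebo. In all three cases the primary deliverable is the same set of summary tables, and 2.8.2 attaches no estimate or test of the difference to it.

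**3. Can change over time stand in?** Let B be the fall in score that a patient would show over a period on the placebo rinse, and D the extra fall on Hydral. The described fall on Hydral is B + D; section 1.3 asks for D. The two agree only if B = 0. Section 1.3 allows B to be above zero. The documents give no value for B or D, so the gap cannot be sized.

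**4. What was N=40 sized for?** For paired proportions (McNemar, normal approximation) with difference d and discordant share psi:

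n = (z_a·√psi + z_b·√(psi − d²))² / d²

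From 2.8.1, d = 0.30, alpha = 0.05 and power = 80%. The discordant share is not given, so it is assumed over a range, two-sided.

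- psi = 0.30: N = 24
- psi = 0.40: N = 33
- psi = 0.48: (1.960 × 0.693 + 0.842 × 0.624)² / 0.09 = 39.4, so N = 40
- psi = 0.60: N = 50
- psi = 0.70: N = 59

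The stated 40 is reached at a discordant share of about 0.48 (one-sided, at 0.60). It is plausible but cannot be uniquely reproduced. It is the size for a between-treatment difference, which is not the primary objective.

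**5. What would N=40 give for a continuous primary score?** For a paired contrast with 40 completers, two-sided alpha 0.05 and 80% power (normal approximation), the detectable difference is (1.960 + 0.842)/√40 = 2.802/6.325 = 0.443 SDs of the within-patient difference. The documents do not give that SD. On a 0-100 score, assumed SDs of 10, 20 and 30 points give 4.4, 8.9 and 13.3 points.

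**The case against.** The strongest reply is that the comparison is already in the plan. Section 1.3 defines the efficacy question as superiority to placebo, 2.4.2 lists efficacy, 2.8.1 sizes the trial on a difference between treatments, and 2.8.2 gives efficacy its own model, separate from the descriptive primary. Read together, the secondary efficacy objective is most naturally Hydral against placebo. That stands. A reader who infers that the plan contains no treatment comparison goes further than the text allows. What the reply does not supply is an outcome, a timepoint or a stated contrast, and at best it places the trial's main question second.

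It can also be said that a descriptive primary is a legitimate choice and agrees with 1.4. True, but it then conflicts with 1.3 and with the basis of the sample size, so the document needs reconciling either way.

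Other inferences should not be drawn:

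- **That a before-after fall on Hydral will be reported as efficacy.** It could be, but 2.4.1 covers all timepoints, which include both products' periods, and nothing says placebo scores will be withheld.
- **That 1.3 contradicts itself about xylitol.** It gives xylitol, as an ingredient, a flavouring role, and then says that water with xylitol may help. The water could supply the relief.
- **That relief on placebo is expected.** The text says only that it may occur, to some extent.
- **That 1.4 seeks a total effect of Hydral which no contrast here can estimate.** It uses no such term.

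**Conclusion.** The point holds as a mismatch between aim, primary objective and design. Sections 1.3 and 1.4 conflict. The primary objective and its analysis follow the descriptive aim, while the design and sample size follow the comparative one. Followed exactly, the plan can meet its primary objective and leave the 1.3 question without a prespecified primary answer.

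This conclusion comes from the wording and depends on no number. Its practical size cannot be stated, because the documents give no expected change on either product; any percentage of Hydral's apparent effect assigned to placebo would be invented. Nor does the point show that N=40 is too small. That figure is compatible with the stated inputs under a reasonable range of discordance, but it belongs to a binary outcome that no objective mentions.

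The change should be made, preferably before any data are seen. It is a correctable weakness in the objectives and does not invalidate the design.

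**What to change.** - **2.4.1:** state as primary the within-patient comparison of Hydral with the water-xylitol placebo on one named xerostomia score, at the end of each treatment period (Day 30 and Day 90). The modified XQ 0-100 summary is one suitable example: 2.4 already defines it, and 2.3.1 already collects it at both visits.
- **2.4.2:** move the description of all questionnaires at all timepoints here, and word the efficacy objective as relative to placebo.
- **1.4:** bring the aim into line with 1.3 by naming the comparator.
- **2.8.2:** replace the sentence that meets the primary objective descriptively with the mixed-model treatment contrast on the chosen score. If this sentence is left, it contradicts the new objective.
- **2.8.1:** state that N=40 was derived for a 30% difference in the proportion improved. Then either keep that proportion as a supporting outcome, or restate what N=40 provides for the new primary under a declared assumption for the SD of within-patient differences.

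The cost is wording in five sections, with no added visits or measurements. There are two small downsides: the primary question can now return a negative answer, and the power statement must be re-expressed. Whether 40 patients are enough for the new primary cannot be settled from the documents, because they do not give that SD.

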2.4.2 SECONDARY OBJECTIVES

- Evaluate Hydral treatment efficacy in reducing xerostomia's symptoms;
- Describe all the adverse events occurred during the study.

2.5 STUDY POPULATION

IDENTIFICATION PARAMETERS

Each patient will be identified with a univocal code (SSHNC-1_n°), which will be known only by the principal investigator.

2.6 RANDOMIZATION

Patients will be randomized to treatment groups using sequentially numbered, opaque sealed envelopes (SNOSE). (23)

The principal investigator will be encharged of generating the allocation sequence, of enrolling the participants and of assigning the interventions to the participants.

The co-workers who will administrate the therapies and the patients themselves will be blinded about the selected product.

Only in case of assessment of any adverse event, it will be possible for the P.I. to reveal the product used during the therapy.

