1.5 EXPERIMENTAL DESIGN

The study will be conducted as a double-blind randomized clinical trial (RCT) and foresees a crossover design, so the population will be divided into two groups, receiving both the medical device and the placebo. The interventions will be described in paragraph 2.3.

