The Investigator should submit any Incident/Near Incident to the Regulatory Authority (Ministero della Salute, Ufficio VI della Direzione Generale dei Dispositivi Medici e del Servizio Farmaceutico, DGDMF, [contact]), to the EC (by e-mail or fax) and to the manufacturer/ authorized representative/distributor following the timelines indicated in the table herebelow:

REPORT	DEADLINE*
--------	-----------

Incident	Within 10 calendar days from the date of knowledge by the Investigator
Near Incident	Within 30 calendar days from the date of knowledge by the Investigator

** to be applied also for Follow-Up reports and for claims to be reported to manufacturer/ authorized representative/distributor.*

This form must be filled in with all the available information, dated and signed.

Upon request by the Regulatory Authorities, the Investigator must complete his/her report with all available follow-up information.

SAFETY FOLLOW-UP

The safety information will be recorded by the Investigator starting from the date of the Informed Consent signature and will end-up at the End of Study Visit.

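### The principal investigator generates the sequence, enrols and assigns, so the sealed envelopes do not assure concealment from that role, and its blinding status is not stated

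*Combined protocol and SAP*

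**What the plan says.** Section 2.6 allocates patients by numbered sealed envelopes and then states: "The principal investigator will be encharged of generating the allocation sequence, of enrolling the participants and of assigning the interventions to the participants". On blinding it says: "The co-workers who will administrate the therapies and the patients themselves will be blinded about the selected product". The only sentence bearing on the PI's own knowledge of the product is: "Only in case of assessment of any adverse event, it will be possible for the P.I. to reveal the product used during the therapy". Section 1.5 labels the trial a double-blind crossover.

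The notes to the flow chart in Section 2.3 give the key from group to product. Note 4: "PHASE A, Group A receives Hydral, Group B receives placebo". Note 5: "PHASE B, Group A receives placebo, Group B receives Hydral".

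Under Safety Follow-up, Section 3.3 says: "The safety information will be recorded by the Investigator starting from the date of the Informed Consent signature". Section 2.7 has data entered on site by the Investigator or someone designated. Section 2.8.2 plans a chi-square comparison of adverse events between the two groups.

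**The concern.** Sealed envelopes hide the next allocation only from people who do not already know the order. Here the author of the order also decides who enters and when. If the PI can anticipate the next sequence, the entry of a given patient can be brought forward, delayed or declined accordingly, even without intent. The two sequences may then differ in the kind of patient they contain.

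The second issue is what the PI knows after allocation. The person who made the list cannot be presumed blinded, and the protocol does not say either way. If that person also records adverse events, knowledge of the product could colour which events are recorded and how they are described.

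**Working it through.** No arithmetic on outcomes applies. The point turns on who does what, and the sample size of 40 in Section 2.8.1 has no bearing on it. The check sets the relevant sections side by side.

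1. **Allocation tasks (Section 2.6).** Generation, enrolment and assignment make 3 tasks. The PI holds 3 of 3.

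2. **Independent custody.** No section names another person to generate the list, fill the envelopes or keep the code. Section 2.6 does not describe how the sequence is generated or how the envelopes are prepared. Section 2.7 mentions a data-management team at the eCRF provider but gives it no part in randomization.

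3. **What a group letter reveals (Section 2.3, Notes 4 and 5).** There are 2 sequences and 2 phases. Group A is Hydral then placebo; group B is placebo then Hydral. One letter fixes the product in both phases, so neutral group labels protect nothing once the letter is known.

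4. **Who is named as blinded (Section 2.6).** Administering co-workers and patients are named: 2 groups. The PI is not among them. The adverse-event sentence fits two readings: the PI discloses a code already held, or the PI opens a code until then unknown. It does not settle the question.

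5. **Where foreknowledge could act.**
   - *Within-patient efficacy contrast.* Each patient is to receive both products, so a difference in patient mix between sequences largely cancels. Section 2.4 rests xerostomia on the patient's own report, and the primary objective in Section 2.4.1 is descriptive. The effect is probably limited.
   - *Comparisons involving sequence.* Selective entry acts directly on order and carry-over, and on any patient who contributes only the first phase and so gives no within-patient contrast.
   - *Adverse events.* Two conditions must both hold for the chi-square test to be affected in a clear direction. First, the PI must be the one recording events. Second, the two groups in Section 2.8.2 must mean products. If they mean sequences A and B, both contain both products, and product-related recording has no evident direction.

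6. **Size.** The documents give no expected adverse-event rate and no basis for a rate of selective entry, so no bias is calculated.

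**The case against.** The strongest reply is that the plan is less exposed than it looks. Several parts of that reply stand.

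- **Envelopes.** A reader might infer that the envelopes cannot conceal anything from the PI. That goes too far. The preparation procedure is not described; a retained list would give foreknowledge, while envelopes shuffled after sealing need not. What the text supports is that concealment from the PI is not assured.
- **The double-blind label.** A reader might infer that Section 2.6 contradicts Section 1.5. It does not: patients and administering staff are named as blinded, which fits the label. The gap is an unstated status.
- **Who records adverse events.** A reader might infer that the PI does. Sections 2.7 and 3.3 say the Investigator, Section 2.7 adds a designee, and Section 6 recognises delegation to staff. PI involvement is possible but not shown.
- **Stopping and revealing.** A reader might see a conflict between Section 2.2, which stops the intervention for events attributable to GUM Hydral, and Section 2.6, which lets the PI reveal the product when an event is assessed. The two are complementary: one can supply information that the other needs.
- **Related matters.** Whether the two liquids look and feel alike, and whether code breaks are logged, are separate questions and do not carry this point.

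What the reply does not answer is the rule itself. Placing all three tasks with one role is an explicit instruction, not a missing detail, and following it as written leaves concealment from that role unsecured.

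**Conclusion.** The point holds in a limited form. Section 2.6 gives 3 of 3 allocation tasks to the PI with no independent custodian, so concealment from the PI is not assured, and the printed key turns knowledge of the group into knowledge of the product in both phases. The PI's blinding status is unstated and blinding cannot be presumed.

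The expected effect on within-patient efficacy is limited. The exposure is selective entry by sequence. Biased adverse-event recording is a further risk only on the assumptions that the PI records events and that the chi-square test compares products. The documents do not show that bias will occur and do not allow its size to be estimated. The change is worth making because it is cheap and because concealment cannot be restored once patients have been allocated.

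**What to change.** Amend Section 2.6 before enrolment so that a party already in the trial, with no role in enrolment or assessment, generates and holds the list and prepares the numbered sealed envelopes or coded kits. A member of the eCRF provider's data-management team who does not clear this trial's data would be suitable. The PI would then only enrol the patient and assign the next number.

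State in Sections 1.5 and 2.6 whether the PI is blinded. The two choices are linked. If the PI opens an envelope showing the group letter, concealment holds up to that moment, but the key in Section 2.3 then reveals the product. Coded kits need not reveal the letter.

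**Cost:** a rewritten paragraph in Section 2.6, a sentence in Section 1.5 and a small set-up task for envelopes or kit numbers. The documents do not show that the eCRF provider has agreed to this role, so that must be arranged. No extra patients or visits are needed.
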